### **D.2 Study population**

Patients with gastric infection by *H. pylori*, diagnosed by C-urea breath test or histological analysis of gastric biopsies and clinical indication for its eradication.

### **D.3 Study design**

This project will be carried out in 4 distinct phases:

**Phase 1.** Recruitment and randomization of patients by the different *H. pylori* eradication schemes (5 parallel arms)

A total of patients with gastric infection by *H. pylori* and clinical indication for its eradication, who have never had previous *H. pylori* eradication therapy, referred to the Gastroenterology Departments of the different participating Portuguese hospital centres (Centro Hospitalar e Universitário de Coimbra, Francisco Gentil Portuguese Oncology Institute of Coimbra and Leiria Hospital Centre), will be included in the study. Patients' selection will take into account the inclusion and exclusion criteria and the minimum number of patients required in order to obtain statistical power. Inclusion criteria: Gastric infection by *H. pylori*. *H. pylori* status will be determined by histological examination of gastric biopsies or carbon 13-labeled urea breath test. The breath test will be considered positive if [CO2] exceeds the baseline value by > 4 parts per thousand (> 0.4%) after 30 minutes. Histological examination for *H. pylori* will be considered positive when this bacterium is detected in ≥1 biopsies (staining with hematoxylin-eosin, modified Giemsa and/or Warthin-Starry). Exclusion criteria: Age < 18 years; Pregnant, breast-feeding or women of childbearing age who do not comply with effective contraception measures; History of allergy, hypersensitivity or contraindication to the use of *H. pylori* eradication drugs (antibiotics or proton pump inhibitors); History of previous gastrointestinal

surgery or neoplasia; Previous H. pylori eradication therapies; Antibiotic or probiotic therapies in the month prior to recruitment; Use of proton pump inhibitors, other antacids or gastric mucosal protection agents in the 2 weeks prior to recruitment; Corticosteroids or immunomodulatory therapy in the month prior to recruitment; Immunodeficiency; Insulin-treated diabetes mellitus; Obesity (Body mass index  $\geq 30\text{Kg/m}^2$ ); Use of laxative therapy in the 15 days prior to recruitment; Decompensated heart, liver, kidney or respiratory diseases and; Refusal or inability to give informed consent. H. pylori eradication schemes: Each patient will randomly follow one of the five H. pylori eradication schemes (5 parallel arms): sequential, hybrid, concomitant with bismuth and two concomitants bismuth-free. Sample size calculation: Assuming the estimated prevalence of H. pylori gastric infection in Portugal in adults is 86.4%, it was determined that for a 95% confidence level and a 10% sampling error it will be necessary to include 46 patients in each of the 5 arms of the study, making a total of 230 patients.

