## Literature Review

*Helicobacter pylori* (*H. pylori*) infection remains a major public health problem, affecting over 50% of the worldwide population and 60-86.4% of the Portuguese population. This bacterium is responsible for chronic active gastritis, likely to develop into peptic ulcerative disease, atrophic gastritis, gastric adenocarcinoma and mucosal-associated lymphoid tissue lymphoma. Factors involved in the development of these conditions include bacterial virulence, host genetic factors and gut microbiota. *H. pylori* eradication therapy has been shown to be effective in preventing the development or recurrence of these complications. However, the increase in primary and secondary resistance of this bacterium to most antibiotics has reduced the efficacy of this therapeutic strategy. As in the rest of Europe, overall resistance to multiple antibiotics is high in Portugal, with a prevalence of 42-50% for clarithromycin, 25-34.4% for metronidazole, 18-33.9% for levofloxacin, 0.2-0.6% for tetracycline, 0.1-0.6% for amoxicillin and 20% for clarithromycin and metronidazole. Taking into account the pattern of *H. pylori* antibiotic resistance in Portugal and the selection flowchart proposed by [GrLeWu14], the currently recommended therapeutic regimens include quadruple therapies: sequential, hybrid, concomitant with bismuth and concomitant bismuth-free. However, some studies including quadruple schemes have shown unsatisfactory results, not exceeding 90% considered as the minimum efficacy rate. Given the high rate of resistance of *H. pylori* to nitroimidazoles registered in Portugal, it would be worth considering therapeutic optimization with metronidazole 500mg tid and not only bid. Thus, at present, there are no solid data that allow us to state the best therapeutic option in this country, being essential to conduct a randomized study to definitively resolve this uncertainty. Animal and human studies have shown that *H. pylori* results in changes in gut microbiota. Human gut microbiota represents a dynamic and complex ecosystem in close linking with the immune system, regulating gastrointestinal homeostasis. It is composed mostly of Gram-negative anaerobic bacilli, mainly Bacteroidetes and Fusobacteria. Gut dysbiosis has been associated with immune, metabolic, nutritional and oncological changes, such as the development of several gastrointestinal and systemic conditions such as inflammatory bowel disease, obesity, diabetes mellitus, metabolic syndrome, dyslipidemia, asthma and allergies. However, the interactions between *H. pylori*, gut microbiota and host pathophysiology are still far from being understood. Similarly, there are also uncertainties regarding the potential negative impact of indiscriminate use of *H. pylori* eradication therapy on the gut microbiota, mediated by either proton pump inhibitors or antibiotherapy. In some recent studies, eradication of *H. pylori* has been associated with a decrease in butyrate-producing bacteria (such as *Faecalibacterium prausnitzii*), Proteobacteria, Actinobacteria and Firmicutes, and an increase in several potentially harmful bacteria such as Bacteroidetes and the Bacteroidetes:Firmicutes ratio. These changes persist until 12-18 months after *H. pylori* eradication therapy, although in one study changes in gut microbiota

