## **Plan and Methods**

### **A. Research hypothesis**

The authors hypothesize that there are relevant differences in the quadruple schemes that can be used in the *H. pylori* eradication therapy, being necessary to define which of them is the most effective in Portugal, in order to decrease the failure rate and subsequent exposure to potentially harmful effects of antibiotics. Additionally, the authors assume that homeostasis of gut microbiota is significantly changed after *H. pylori* eradication therapy and these alterations may not be similar among the different recommended therapeutic regimens. Likewise, these alterations may have clinical implications in the immunological, metabolic and nutritional status of individuals submitted to this therapy. Hypothesis: There is a quadruple *H. pylori* eradication therapy associated with a higher efficacy and safety than other currently approved quadruple regimens in terms of clinical, immunological and microbiota changes in *H. pylori* gastric infection.

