### **B. Objectives**

- To determine and compare the efficacy of the different therapeutic regimens recommended as *H. pylori* eradication therapy;
- Comparative evaluation of the safety profile in terms of clinical, immunological and gut microbiota impact of the different recommended therapies for the *H. pylori* eradication:
- To evaluate the changes in gut microbiota after the *H. pylori* eradication therapy;
- Compare the changes in gut microbiota induced by the different therapeutic regimens for *H. pylori* eradication and evaluate their clinical implications on immunology, nutrition and metabolism;
- To evaluate the immunological changes after the *H. pylori* eradication therapy;
- Compare the immunological changes induced by the different therapeutic regimens for *H. pylori* eradication and evaluate their clinical implications.

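### The 46 patients per arm are derived from the population prevalence of H. pylori infection, which the trial never estimates, so the size has no stated link to eradication rates, a between-arm difference or power.

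*Combined protocol and SAP*

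**What the plan says.** The sample-size paragraph in D.3 Study design (Phase 1) reads: "Assuming the estimated prevalence of H. pylori gastric infection in Portugal in adults is 86.4%, it was determined that for a 95% confidence level", adds a 10% sampling error, and concludes that "it will be necessary to include 46 patients in each of the 5 arms of the study, making a total of 230 patients". Nothing else is offered as a basis for the number.

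Other parts of the document bear on it:

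- The Literature Review gives the source range of the input: infection affects "60-86.4% of the Portuguese population". The value used is the top of that range.
- Section D.2 and the entry criteria in D.3 ("Inclusion criteria: Gastric infection by" H. pylori) restrict the trial to patients who are already infected.
- Section B sets the first objective: "To determine and compare the efficacy of the different therapeutic regimens". Section A speaks of "being necessary to define which of them is the most effective in Portugal".
- D.3 says that patient selection will take into account "the minimum number of patients required in order to obtain statistical power". No power value appears in the supplied text.
- D.4 compares categorical variables by chi-squared test at p < 0.05.
- The Literature Review gives one efficacy benchmark, saying that some studies of quadruple regimens had results "not exceeding 90% considered as the minimum efficacy rate". The sample-size paragraph does not use it.

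**The concern.** A sample size should follow from the quantity the trial estimates or tests. Here the quantity is eradication, compared across five arms. The proportion in the formula is how common infection is among Portuguese adults. In this trial that proportion is 100% by design, so the calculation fixes the precision of an estimate that will never be made.

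A reader therefore cannot tell what 230 patients can show about the regimens. If power for realistic differences is low, the likely result is a non-significant chi-squared test that says little about which regimen is best and may be misread as showing that the regimens perform alike.

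**Working it through.** **1. Reproducing the plan's figure.** Inputs from D.3: p = 0.864, z = 1.96 (95% confidence), d = 0.10 (the 10% sampling error, read as an absolute half-width).

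n = z² p(1 − p) / d² = 1.96² × 0.864 × 0.136 / 0.10² = 45.1, rounded up to 46; 46 × 5 = 230.

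Both figures match, so there is no arithmetic error.

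**2. Sensitivity to the input.** With the lower end of the cited prevalence range, p = 0.60: 1.96² × 0.60 × 0.40 / 0.10² = 92.2, rounded up to 93; 93 × 5 = 465. A quantity unrelated to the aim could have doubled the trial.

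**3. What 46 per arm delivers.** The documents give no expected eradication rates. I assume 80–95% for the better arm, chosen to bracket the 90% benchmark. I also show 41 evaluable per arm, which assumes 10% loss (46 × 0.9 = 41.4). Intervals are Wilson for one arm and Newcombe for a difference between two arms with equal rates.

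| 95% half-width, points | 80% | 85% | 86.4% | 90% | 95% |
|---|---|---|---|---|---|
| One arm, n = 46 | 11.3 | 10.3 | 9.9 | 8.9 | 7.0 |
| One arm, n = 41 | 12.0 | 10.9 | 10.5 | 9.4 | 7.5 |
| Difference, n = 46 | 16.4 | 15.0 | 14.6 | 13.3 | 11.0 |
| Difference, n = 41 | 17.3 | 16.0 | 15.5 | 14.2 | 11.9 |

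**4. Pairwise power.** The test is the pooled two-proportion z-test, equivalent to the 2×2 chi-squared test without continuity correction, at two-sided 0.05. Power is the sum of the binomial probabilities of all outcomes that reject. At n = 46 the actual size of this test is 0.050–0.059.

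| Power, by better arm's rate | 80% | 85% | 90% | 95% |
|---|---|---|---|---|
| 10 points, n = 46 | 19% | 23% | 28% | 39% |
| 15 points, n = 46 | 36% | 41% | 49% | 64% |
| 20 points, n = 46 | 56% | 61% | 70% | 82% |
| 10 points, n = 41 | 18% | 21% | 25% | 36% |
| 20 points, n = 41 | 51% | 57% | 65% | 77% |

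**5. Difference detectable with 80% power.** Five arms give 5 × 4 / 2 = 10 pairs, so the Bonferroni level is 0.05 / 10 = 0.005.

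| Points, by better arm's rate | 95% | 90% | 85% | 80% |
|---|---|---|---|---|
| n = 46, level 0.05 | 19.3 | 23.3 | 25.6 | 27.1 |
| n = 46, level 0.005 | 28.4 | 32.2 | 34.6 | 36.2 |
| n = 41, level 0.05 | 20.9 | 24.8 | 27.3 | 28.8 |
| n = 41, level 0.005 | 31.0 | 34.8 | 37.1 | 38.5 |

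**6. Five-arm chi-squared test** (46 per arm, 400,000 simulations per scenario). Each range runs over the arm or arms with the higher rate at 80%, 90% and 95%.

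| Scenario | Power |
|---|---|
| One arm better by 10 points | 15–23% |
| One arm worse by 10 points | 18–39% |
| One arm better by 20 points | 52–75% |
| One arm worse by 20 points | 58–88% |
| Rates 95/90/85/80/70% | 83% |

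**7. Size needed for one unadjusted 10-point pairwise comparison at 80% power**, by the same enumeration and with no allowance for loss: 133 per arm (95% v 85%), 196 (90% v 80%) or 292 (80% v 70%). Over five arms that is 665, 980 or 1,460. The usual normal-approximation formula gives similar answers, for example 199 per arm for 90% v 80%.

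**The case against.** The best defence is that the formula can be read as a precision calculation for each arm. If eradication happened to be 86.4%, 46 patients would give that arm's rate to within 9.9 points, close to the stated 10. At higher rates the precision is better still; it falls short of 10 points only below about 86% (below about 88% with 41 evaluable). That would serve the part of the objective that concerns determining efficacy. But the protocol does not present the number this way, and precision per arm does not size a comparison: between two such arms the half-width is 14.6 points.

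Second, D.4 refers further efficacy analysis to a Tasks section that is not in the text supplied. That limit is real, and differences with confidence intervals may already be planned there. However, D.4 cites that section for analysis, and the sample-size paragraph gives a complete derivation without referring to it.

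Third, the trial is not powerless. The five-arm test does well against some large differences, such as 88% power when four arms are at 95% and one at 75%. This stands, but it does not help with 10-point differences, or with a single arm that is better by 20 points, where power is at most 75%.

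Fourth, the eradication range, the 10% loss and the Bonferroni correction are not the sponsor's figures, and rewording adds no power. Both points are fair. The sponsor should substitute its own assumptions where it has them, and the wording below claims only to disclose.

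**Conclusion.** The sample-size basis is wrong as written, not merely short of detail, and must be corrected. The only justification given targets a quantity that the trial cannot estimate, and the protocol refers to statistical power that it neither states nor calculates.

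Under the assumed rates, a true 10-point difference between two regimens would be missed more often than found, and a 20-point pairwise difference reaches 80% power only when the better arm is near 95%. The mismatch between prevalence and eradication rests on the text alone. The power figures rest on assumed rates, but power for 10 points stays below 40% throughout the range, for pairwise tests and in the five-arm scenarios examined. The check covers eradication efficacy only, not the microbiota or immunological comparisons.

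**What to change.** 1. **D.3, Phase 1, patient selection:** remove the reference to a number needed for power.

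2. **D.3, sample-size paragraph:** replace the prevalence justification. Example, to be adapted to the sponsor's own assumptions:

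> The planned sample size is 46 per arm (230 in total); it was not derived from a between-arm comparison. With 46 evaluable patients per arm, the 95% CI half-width is about 11 to 7 points for an arm's eradication rate of 80% to 95% (Wilson), and about 16 to 11 points for the difference between two arms with equal rates in that range (Newcombe). If the better arm's rate is 95% to 80%, a pairwise difference of about 19 to 27 points is detectable with 80% power (pooled two-proportion test, two-sided 0.05, power by enumeration), or about 28 to 36 points with Bonferroni correction for 10 pairs. With an assumed 10% loss (41 evaluable per arm) these figures become about 12 to 7.5, 17 to 12, 21 to 29 and 31 to 38.5 points.

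3. **D.4:** add the following, unless the Tasks section already provides for it.

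> Efficacy comparisons will be reported as differences with 95% CIs alongside the chi-squared test, and a non-significant result will not be read as equivalence.

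The cost is wording in two places in D.3 and one sentence in D.4, with no extra patients. It makes the limited power visible but does not raise it. If the sponsor wants the trial to separate regimens that differ by about 10 points, it must re-size on a stated difference (665 to 1,460 patients in five arms under the assumptions above, before multiplicity or loss). Limiting the number of comparisons would reduce the multiplicity penalty. Either is for the sponsor to decide.

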#### **Phase 2.** Eradication of H. pylori and collection of stool and blood samples

Stool samples shall be collected from patients and analyzed on 3 occasions: before (baseline), after stopping treatment (Day 10 or 14) and 1 month after treatment (Day 40 or 44). Blood samples will be collected and analyzed on 2 occasions: before (baseline) and 12 months after treatment. Efficacy and safety rates of H. pylori eradication will be determined for each therapeutic regimen. Carbon 13-labeled urea breath test or upper gastrointestinal endoscopy with biopsies will be performed at 1 month (D40 or D44) and 12 months after treatment. The clinical data, adherence and therapy-related adverse events will be recorded at baseline and during follow-up at 1 and 12 months post-eradication.

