## **D. Methodology and Phases of project development**

### **D.1 Type of study**

Prospective longitudinal multicentre study and a blind randomized controlled trial involving several hospital units in Portugal. Regarding the evaluation of gut microbiota and immunological changes, the study will be blinded, since the researchers responsible for sequencing and immunological analysis will not know the therapeutic scheme applied. The trial will be registered on the <https://clinicaltrials.gov> platform.

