#### **Phase 3.** Analysis of gut microbiota changes by DNA sequencing after H. pylori eradication therapy and their clinical impact on immunology, metabolism and nutrition

The impact of H. pylori eradication therapy on gut microbiota will be studied by next generation genome sequencing techniques. A comparative analysis will be performed for each therapeutic regimen used. Microbiota changes found will be compared with clinical and analytical data in order to establish their impact on immunology, metabolism and nutrition status at 1 and 12 months post-eradication. Phase 4. Analysis of immunological changes of cell populations, cytokines, chemokines and growth factors after H. pylori eradication therapy and their clinical impact. The impact of H. pylori eradication therapy on humoral and cellular immunity will be studied by flow cytometry and xAMP/Luminex. A comparative analysis will be performed for each therapeutic regimen used. Immunological changes found will be compared with clinical and analytical data in order to establish their clinical impact at 12 months post-eradication.

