#### **D.4 Statistical Analysis**

Using the Statistical Package for the Social Sciences (SPSS) version 22.0 (IL, USA). The level of statistical significance will be for a p-value  $< 0.05$ . The normality of data distribution will be evaluated by Kolmogorov-Smirnov or Shapiro-Wilk tests. Continuous variables will be expressed as mean and standard deviation or median and interquartile range and categorical variables as frequency and percentage. The comparison of continuous variables will be made using the Kruskal-Wallis test or Anova test and categorical variables using the Chi-squared test. For the comparison of paired data the Wilcoxon test or Friedman test and the t-Student or Anova test will be used. Further statistical analysis of H. pylori eradication efficacy, gut microbiota and immunological changes is described in Tasks section. The genome sequences will be grouped in OTU according to their similarity. The alpha taxonomic richness and diversity of fecal samples will be expressed in observed species, Sobs index and Shannon index. The composition of fecal

microbiota will be expressed in rarefaction curves and the comparison of the differences in OTU richness with the t-Welch test. Immunological findings will be expressed by radar charts and representative FACS dot-plots. Additional statistical analyses will be defined throughout the study.

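### The before-after effect of eradication therapy on immunity has no comparator except each patient's own baseline, so a shift between assay periods about a year apart could be reported as a therapy effect

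*Combined protocol and SAP*

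**What the plan says.** **Arms.** D.3 Phase 1: "Each patient will randomly follow one of the five H. pylori eradication schemes (5 parallel arms): sequential, hybrid, concomitant with bismuth and two concomitants bismuth-free". No untreated, deferred-treatment or uninfected group is described.

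**Question.** B. Objectives includes a before-after aim ("To evaluate the immunological changes after the" eradication therapy), followed by a separate item comparing regimens. The Phase 4 text in D.3 makes the same distinction. It first says "The impact of H. pylori eradication therapy on humoral and cellular immunity will be studied by flow cytometry and xAMP/Luminex", and then "A comparative analysis will be performed for each therapeutic regimen used".

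**Blood sampling.** D.3 Phase 2: "Blood samples will be collected and analyzed on 2 occasions: before (baseline) and 12 months after treatment". The Abstract also places the flow cytometry and Luminex work before therapy and 12 months after it.

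**Analysis.** D.4: "For the comparison of paired data the Wilcoxon test or Friedman test and the t-Student or Anova test will be used". It mentions no term for assay run, reagent lot or calendar time. The significance level is 0.05.

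**Blinding.** D.1 says that "the researchers responsible for sequencing and immunological analysis will not know the therapeutic scheme applied". Blinding to the time point of the sample is not mentioned.

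The text does not describe sample storage, same-run assay of paired samples, bridging samples or reference controls.

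**The concern.** The plan asks two different immunological questions. Whether regimens differ is answered by randomised arms. Whether eradication therapy as such changes immunity is answered only by comparing each patient after therapy with the same patient before it. In that second comparison, anything that differs between the two assay periods is added to the change: a new reagent lot, instrument recalibration, or a change of operator or plate. So is anything that differs with time itself, such as season, ageing or regression to the mean. A paired test cannot tell these apart from a therapy effect.

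At stake is whether a stated objective gives an interpretable result. Pooling 230 patients makes the paired test sensitive to small shifts, whatever their cause. The choice also has to be made before samples are processed: if no baseline aliquot is kept, it cannot later be re-run beside its follow-up.

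**Working it through.** **1. The plan's own figure.** D.3 Phase 1 uses a proportion of 0.864, 95% confidence and a 10% sampling error:

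n = 1.96² × 0.864 × 0.136 / 0.10² = 45.14, rounded up to 46 per arm; 46 × 5 = 230.

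This reproduces exactly. It is a precision calculation for one proportion and gives no power for an immune marker.

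**2. Inputs for the check.**
- From the documents: N = 230 pooled, 46 per arm; significance level 0.05, taken as two-sided because sidedness is not stated.
- Assumptions, because the documents give no figure: a common shift s between assay periods of 0.05, 0.1 or 0.2 marker SD; within-patient correlation r of 0.4 to 0.8; no dropout; no true therapy effect.

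**3. Formula.** The SD of the within-patient change is √(2(1−r)) marker SD. The standardised shift is d = s / √(2(1−r)), and the noncentrality of the paired t-test is d√N. The probability of p < 0.05 then comes from the noncentral t distribution.

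Example, s = 0.2 and r = 0.6: SD of change = √0.8 = 0.894; d = 0.2/0.894 = 0.224; noncentrality = 0.224 × √230 = 3.39; false significance in 92%. Within one arm of 46, noncentrality = 0.224 × √46 = 1.52; false significance in 32%.

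**4. Range, 230 patients pooled.**

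| Shift (marker SD) | r = 0.4 | r = 0.6 | r = 0.8 |
|---|---|---|---|
| 0 | 5% | 5% | 5% |
| 0.05 | 11% | 13% | 22% |
| 0.1 | 28% | 39% | 67% |
| 0.2 | 79% | 92% | nearly 100% |

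With 20% dropout (184 patients; assumption), the case s = 0.2 and r = 0.6 gives 85%.

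**5. If run errors are independent.** Suppose there is no steady drift. Each run has its own error with SD 0.2 (assumption), and each time point is spread over K runs. The net shift then has SD 0.2 × √(2/K), for example 0.09 with K = 10. With r = 0.6 and N = 230, false significance is about 49% for K = 3, 23% for K = 12 and 14% for K = 24. The problem shrinks with more runs but stays above 5% in these cases.

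**6. Between-regimen comparison.** In 10,000 simulated trials of 5 × 46 patients, a one-way ANOVA of the change scores rejected in 4.6% to 5.1% for common shifts of 0 to 0.5 SD of the within-patient change. A shift shared by all arms cancels.

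**7. Same-run assay.** If both samples of a patient are on one plate, a shift common to that plate drops out of the difference (s = 0), and the rate returns to 5% as far as assay shift is concerned.

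**The case against.** **Assay timing is inferred.** The Phase 2 sentence lists sampling time points, not assay dates. The four-phase layout puts sample collection in Phase 2 and the laboratory work in Phases 3 and 4, which fits a later batched assay. This stands in part. Batching is possible, but the sentence couples collection and analysis on each occasion, and no storage is described. If batching is intended, one sentence would settle it for stored serum or plasma.

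**Confounding need not be complete.** A reader might infer that assay run and time point are fully confounded and that nothing in the design can remove a shift. The documents do not support that. Recruitment duration is not given. With staggered enrolment each time point spans many runs, and if enrolment exceeds 12 months, early follow-ups overlap late baselines. D.4 also refers to a Tasks section for further immunological analysis. That section is not in the text available, so a safeguard there cannot be ruled out.

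**The magnitude rests on assumed inputs.** This is correct. The result runs from 5% with no shift to nearly 100% at 0.2 SD, so only a range is meaningful.

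**The consequence is secondary.** The hypothesis in section A is comparative, and the before-after items in B follow a heading about comparative safety. Efficacy and the regimen comparison are untouched. This limits the importance of the point. It does not remove it, because Phase 4 states the effect of therapy on immunity as a question in its own right.

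**Stool.** A reader might extend the point equally to the microbiota samples. Those run from baseline to Day 40 or 44, about six weeks, so the case is much weaker.

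**Conclusion.** The point holds as a risk to one stated aim, not as a demonstrated bias. All arms are active, the only comparator for the pooled immunological change is the patient's own baseline, the two assays are on the plain reading about 12 months apart, and the planned paired tests carry no term for run.

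With no true effect, the pooled paired test would be falsely significant in 11-22%, 28-67% or 79-100% of cases for a systematic shift of 0.05, 0.1 or 0.2 SD, against a nominal 5%. This assumes a correlation of 0.4 to 0.8 and no dropout. The actual shift is unknown, and independent run errors over many runs give lower rates.

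A reader might infer that the regimen comparison is compromised as well. It is not biased by a shift common to all arms, provided the arms are recruited concurrently and assayed alike.

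**What to change.** **D.3 Phase 2.** Say that blood is collected, rather than collected and analysed, on the two occasions. Store serum or plasma aliquots from both visits. Run each patient's baseline and 12-month samples on the same Luminex plate, with the five arms spread across plates. Where flow cytometry needs fresh cells, run a fixed control material at every session and report the shift between periods.

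**D.3 Phase 4.** State that only differences between regimens are attributed to treatment, and that the pooled before-after change is reported as a change over time. This second change is needed even with same-run assay, which does not remove season, ageing or regression to the mean.

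**Optional.** Same-run sequencing of each patient's stool samples, as a lesser point.

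**Cost.** No extra patients or visits and the same number of patient-sample assays, plus the control material for cytometry. It needs freezer space for about a year and a plate-layout rule, and baseline results arrive later. Baseline aliquots will be stored longer than follow-up aliquots. This is itself a before-after difference and should be reported as a limitation. Cytometry on fresh cells is only partly protected.
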